7.3.3.3 Exclusions for Analyses of MCMs

In the final report, analyses of MCMs will exclude the following:

- Pregnancies among women exposed to known teratogens from 5 half-lives (specific for each teratogen) prior to ECD through the end of pregnancy ([Winterstein et al., 2024](#)). A list of teratogens can be found in [Appendix B](#).
- Pregnancies among women who are diagnosed with a TORCH infection (toxoplasmosis, other [syphilis, varicella-zoster, parvovirus B19, human immunodeficiency virus {HIV}], rubella, cytomegalovirus, and herpes simplex) during pregnancy because they are known to cause congenital anomalies ([Neu et al., 2015](#)).
- Infants with syndromic or chromosomal anomalies identified during pregnancy or at birth (i.e., Down syndrome, trisomies 18 and 13, and other trisomies; monosomies and deletions from the autosomes; balanced re-arrangements and structural markers; and Turner's syndrome, other sex chromosome abnormalities, and other chromosomal abnormalities).

Code lists for these exclusions will be provided in the statistical analysis plan (SAP).

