7.2.2 Optum's Market Clarity Data

Beginning with the 2029 PSUR, patients will also be identified within Optum's Market Clarity Data. This database integrates medical and pharmacy claims data with clinical data for approximately 80-85% of patients in Optum's EHR Research Database from January 2007 through the present. Market Clarity includes data on over 82 million patients as of March 2024, with over 68 million of those having eligibility information available.

Optum's EHR Research Database is a patient-level database that integrates multiple electronic medical record data systems with medical billing, prescription, and practice management data. The database incorporates relevant clinical data, as recorded during routine clinical practice, for patients in both ambulatory and inpatient settings. Data include medical records, laboratory results, and drug prescription (including number of refills) and administration data.

The database also includes data derived from free-text clinical notes relating to the medical encounters. Optum uses a generalized natural language processing (NLP) system developed to extract and organize concepts from free text into semi-structured fields. The database contains pertinent attributes, sentiments, and modifiers to the concepts. Re-examination of the source text

corresponding to the NLP-extracted observations is possible with appropriate permissions.

In Market Clarity, Optum's EHR data are supplemented with medical and pharmacy claims from the ORD and from third-party data sources. The availability of linked pharmacy claims data in Market Clarity provides the opportunity to augment the data on drug prescriptions available in the EHR, which enables more comprehensive identification of all drugs received by patients through pharmacy drug dispensings. This linkage will accordingly improve the ability to capture nemolizumab initiation and subsequent drug dispensings within the database.

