Cohort entry will be set at the date of dispensing in the Nemolizumab Cohort (i.e., the earliest nemolizumab administration date during a pregnancy) and the Other AD/PN Treatment Cohort,

and the corresponding day of gestation among unexposed pregnancies, rounded down to the nearest week. For example, for pregnancies entering the Week 8 Cohort, we will first select all pregnancies with no nemolizumab or other AD/PN treatment from 5 times the half-life before ECD through 7 weeks' + 6 days' gestation. Then, we will assign the pregnancies that receive nemolizumab during Week 8 (8 weeks + 0 days through 8 weeks + 6 days) to the nemolizumab-exposed group, those that received another AD/PN treatment to the other treatment-exposed group, and those that did not receive nemolizumab or another AD/PN treatment during Week 8 to the unexposed group. Cohort entry among the Week 8 nemolizumab and comparator cohorts will be set to 8 weeks' + 0 days. The pregnancies in the Week 8 exposed cohort will no longer be eligible for inclusion in subsequent weekly cohorts. However, the pregnancies in the Week 8 unexposed group will go on to be eligible for inclusion in the Week 9 Cohort, at which point their exposure status would be reassessed during Week 9 (9 weeks + 0 days through 9 weeks + 6 days). A pictorial depiction of this process can be found in Figure 1 and key pregnancy dates can be found in Table 1. If the study size does not permit weekly sequential cohorts, the cohorts may be collapsed into longer (e.g., 2-week, 4-week) intervals as needed.

Figure 1 Sequential cohort design, depicting an example of cohort entry for the Week 7 and Week 8 cohorts

Abbreviations: AD, atopic dermatitis; ECD, estimated conception date; PN, prurigo nodularis

Table 1 Pregnancy dates

Date	Definition
LMP	First day of last menstrual period 0 gestational weeks ^{0/7 days}
Gestational age	Weeks of gestation Anchored by LMP Number of completed weeks elapsed after LMP

Date	Definition
ECD	Estimated as LMP + 14 days 2 gestational weeks ^{0/7 days}
First trimester	Begins at ECD minus 5 times the half-life of the treatment Ends at LMP + 97 days
Second trimester	Begins at LMP + 98 days Ends at LMP + 195 days
Third trimester	Begins at LMP + 196 days Ends at pregnancy outcome
Pregnancy period	Begins at ECD minus 5 times the half-life of the treatment Ends at pregnancy outcome

Abbreviations: ECD, estimated conception date; LMP, first day of last menstrual period

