7.3.6.2 Etiologically Relevant Windows for Exposure Assessment

For most study outcomes, the analysis will include weekly exposure cohorts that are formed throughout pregnancy (i.e., approximately 40 potential weekly cohorts beginning at Week 2 through Week 40 or the latest observed week of gestation). However, analyses of spontaneous abortion and elective termination will be restricted to the Week 2-19 Cohorts, because spontaneous abortion is defined as a pregnancy loss occurring before 20 weeks' gestation, and all pregnancies that are ongoing at Week 20 will be censored in these analyses. Analyses of preterm birth will be restricted to Weeks 2-36 Cohorts, because preterm birth is defined as a livebirth occurring before 37 weeks' gestation, and analyses of ectopic pregnancy and MCMs will be restricted to Weeks 2-13 Cohorts.

Table 2 depicts the potential gestational weeks of cohort entry for each study outcome relative to the timing of outcome assessment.

Table 2 Etiologically relevant exposure windows for study outcomes

Study Outcome	Etiologically Relevant Exposure Window	Potential Cohort Entry of Pregnancy	Start of Follow-up¹	Censoring Events²
Ectopic pregnancy	First trimester	Week 2 – Week 13	Cohort entry	End of pregnancy, disenrollment from the health plan/8 weeks of no clinical activity, or the end of the study period
Elective termination	ECD through 19 weeks' gestation (19 weeks + 6 days)	Week 2 – Week 19	Cohort entry	20 weeks + 0 days, end of pregnancy, disenrollment from the health plan/8 weeks of no clinical activity, or the end of the study period
Live births	Entire pregnancy	Week 2 – Week 40	Later of cohort entry or 20 weeks + 0 days	End of pregnancy, disenrollment from the health plan/8 weeks of no clinical activity, or the end of the study period
Preterm birth	ECD through 36 weeks' gestation (36 weeks + 6 days)	Week 2 – Week 36	Later of cohort entry or 20 weeks + 0 days	37 weeks + 0 days, end of pregnancy, disenrollment from the health plan/8 weeks of no clinical activity, or the end of the study period

Study Outcome	Etiologically Relevant Exposure Window	Potential Cohort Entry of Pregnancy	Start of Follow-up ¹	Censoring Events ²
Spontaneous abortion	ECD through 19 weeks' gestation (19 weeks + 6 days)	Week 2 – Week 19	Cohort entry	20 weeks + 0 days, end of pregnancy, disenrollment from the health plan/8 weeks of no clinical activity, or the end of the study period

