7.4.2.2 Infant Outcomes

7.4.2.2.1 MCM

MCMs will be defined based on guidelines from the New York State Department of Health Congenital Malformations Registry, National Birth Defects Prevention Network, and/or the European Surveillance of Congenital Malformations. Live births will be followed for up to one year to identify MCMs that may not be detected until after birth. All identified MCMs will be counted, overall, and classified by body system. Operational definitions may be modified to add or remove MCM-specific ICD-10-CM codes based on clinician input or newly identified algorithms in the literature. Minor congenital malformations will not be included in this definition. A list of ICD-10-CM diagnosis codes for MCMs can be found in [Appendix E](#).

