Outcome	Type	Code(s)	Code Description
Elective termination	ICD-10 Procedure	10A04ZZ	Abortion of Products of Conception, Perc Endo Approach
Elective termination	ICD-10 Procedure	10A07Z6	Abortion of Products of Conception, Vacuum, Via Opening
Elective termination	ICD-10 Procedure	10A07ZW	Abortion of Products of Conception, Laminaria, Via Opening
Elective termination	ICD-10 Procedure	10A07ZX	Abortion of POC, Abortifacient, Via Opening
Elective termination	ICD-10 Procedure	10A07ZZ	Abortion of Products of Conception, Via Opening
Elective termination	ICD-10 Procedure	10A08ZZ	Abortion of Products of Conception, Endo
Elective termination	HCPCS	S0190	Mifepristone Oral 200mg
Elective termination	HCPCS	S0191	Misoprostol, oral, 200 mcg
Elective termination	HCPCS	S0199	Medically induced abortion by oral ingestion of medication including all associated services and supplies (e.g., patient counseling, office visits, confirmation of pregnancy by HCG, ultrasound to confirm duration of pregnancy, ultrasound to confirm completion of abortion) except drugs
Elective termination	HCPCS	S2260	Induced abortion, 17-24 weeks
Elective termination	HCPCS	S2265	Induced abortion, 25-28 weeks
Elective termination	HCPCS	S2266	Induced abortion, 29-31 weeks
Elective termination	HCPCS	S2267	Induced abortion, 32 weeks/greater
Elective termination	CPT ⁵	01965	Anesthesia for incomplete or missed abortion procedures
Elective termination	CPT	01966	Anesthesia for induced abortion procedures
Elective termination	CPT	59840	Induced abortion, by dilation and curettage
Elective termination	CPT	59841	Induced abortion, by dilation and evacuation
Elective termination	CPT	59850	Induced abortion, by 1 or more intra-amniotic injections (amniocentesis-injections), including hospital admission and visits, delivery of fetus and secundines;
Elective termination	CPT	59851	Induced abortion, by 1 or more intra-amniotic injections (amniocentesis-injections), including hospital admission and visits, delivery of fetus and secundines; with dilation and curettage and/or evacuation
Elective termination	CPT	59852	Induced abortion, by 1 or more intra-amniotic injections (amniocentesis-injections), including hospital admission and visits, delivery of fetus and secundines; with hysterotomy (failed intra-amniotic injection)

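### The chromosomal/syndromic exclusion for the MCM analysis stops at birth while MCMs are counted for a year; secondarily, the teratogen exclusion runs past the first-trimester MCM window

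*Protocol*

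**What the plan says.** Section 7.3.3.3 of the protocol lists three exclusions that apply only to the MCM analyses, MCM being the primary outcome:

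- Teratogens: "Pregnancies among women exposed to known teratogens from 5 half-lives (specific for each teratogen) prior to ECD through the end of pregnancy". The drugs are in Appendix B.
- TORCH infections diagnosed "during pregnancy because they are known to cause congenital anomalies".
- "Infants with syndromic or chromosomal anomalies identified during pregnancy or at birth", followed by a bracketed list of trisomies, monosomies, deletions, sex chromosome abnormalities and other chromosomal abnormalities.

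Code lists for these exclusions are left to the SAP. The time windows are fixed in the protocol.

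The MCM outcome has its own windows. For ascertainment, Section 7.4.2.2.1 states: "Live births will be followed for up to one year to identify MCMs that may not be detected until after birth". Table 2 agrees, with follow-up from delivery through the first year of life. For exposure, Section 7.3.6.2 states that "analyses of ectopic pregnancy and MCMs will be restricted to Weeks 2-13 Cohorts", and the first-trimester row of Table 1 reads "Ends at LMP + 97 days", counted from the last menstrual period (LMP).

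**The concern.** An exclusion by cause works only if it is applied over the same period in which cases are counted. Here the case window is a year and the exclusion window closes at birth. Two infants with the same chromosomal condition and the same heart defect are handled differently if one is coded at delivery and the other at six weeks: the first leaves the analysis, the second is an MCM case. Cases unrelated to drug exposure then remain in both groups and pull the RR towards 1.

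The teratogen rule has the opposite mismatch. The protocol treats only the first trimester as relevant for nemolizumab and MCM, but a listed drug first dispensed in the second or third trimester still removes the pregnancy. That event comes after cohort entry. Section 7.1 presents the final analysis as a target trial emulation, Section 7.7.3.1 limits propensity score covariates to information from cohort entry or earlier, and Section 7.4.3.6 keeps teratogen exposure during pregnancy out of the propensity score. Using the same later event as an exclusion sits uneasily with those rules. The TORCH exclusion shares this feature.

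**Working it through.** **1. The windows side by side**

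| Item | Starts | Ends | Source |
|---|---|---|---|
| MCM ascertainment | delivery | one year of age | 7.4.2.2.1, Table 2 |
| Chromosomal/syndromic exclusion | pregnancy | birth | 7.3.3.3 |
| MCM exposure window | ECD minus 5 half-lives | LMP + 97 days | Tables 1 and 2 |
| Teratogen exclusion | ECD minus 5 half-lives | end of pregnancy | 7.3.3.3 |

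None of the sensitivity analyses in Sections 7.7.3.5.1 to 7.7.3.5.9 varies either exclusion window.

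**2. Which infants slip through**

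Appendix E contains no Q90–Q99 codes, so a late chromosomal code is not itself an MCM. What counts is the accompanying structural defect, for example a cardiac code in Q20–Q28. Appendix E also lists Q87 (specified malformation syndromes) as MCM. If the word syndromic in 7.3.3.3 is meant to cover that group, a Q87 syndrome first coded after birth is counted as well. The bracketed list names only chromosomal conditions, so that depends on the reading.

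**3. The protocol's own figure**

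Inputs from Section 7.5: comparator prevalence 3%, RR 2.5 (so 7.5% in the exposed), 1:4 ratio, 80% power, two-sided alpha 0.05. The Fleiss formula without continuity correction gives 214 exposed live births, as stated. Then 214 / (0.80 × 0.76) = 352.0 pregnancies, as stated. The size calculation is not in dispute.

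**4. Size of the dilution**

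The protocol gives neither the share of MCM infants with a chromosomal cause nor the share coded late. Assumptions: 5–15% of infants with an MCM code are chromosomal cases, and 20–40% of those are first coded after birth.

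- Low: 0.05 × 0.20 = 1% of counted MCMs; 1% of 3% = 0.03 percentage points.
- High: 0.15 × 0.40 = 6% of counted MCMs; 6% of 3% = 0.18 percentage points.

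Add c to both groups, assuming late-coded cases are equally common in each. Observed RR = (0.075 + c) / (0.03 + c).

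- c = 0.0003: 0.0753 / 0.0303 = 2.49
- c = 0.0018: 0.0768 / 0.0318 = 2.42

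Taking the 3% instead as already containing these cases gives RR = 2.5 − 1.5 × share, that is 2.485 and 2.41, practically the same. With the added c, the Fleiss requirement moves from 214 to 215 and 222 live births. A wider assumption of 0.1–0.3 percentage points gives RR 2.45–2.36 and 218–227 live births.

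**5. Length of the teratogen overhang**

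For an assumed 280-day pregnancy, the days from LMP + 98 to delivery are 280 − 98 = 182. Conception to delivery is 280 − 14 = 266 days, so 182 / 266 = 68% of that time lies outside the MCM exposure window but inside the exclusion window. The protocol has no figure for how many pregnancies have a listed drug only in that stretch, so no loss can be calculated.

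**The case against.** On the chromosomal point, one can say that the effect is small, that Section 7.4.2.2.1 lets MCM codes be added or removed on clinician input, and that the SAP will carry the exclusion code lists. The first is true and sets the priority. The other two do not cure the problem: a code list says which diagnoses count, not until when, and dropping a cardiac code would remove it for every infant. At birth might also be read loosely as the newborn period, but the protocol does not define it so, and even that would fall short of one year.

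On the teratogen point the counter-argument is stronger. Section 7.10 says that the exact timing of malformation development is typically unknown. Table 2 defines the window for the study drugs, not the risk period of each Appendix B drug, some of which may affect the foetus later. Excluding through the end of pregnancy is a cautious choice, in line with the TORCH and JAK inhibitor exclusions. No difference by nemolizumab exposure has been shown. This stands as a reason not to replace the main rule. It does not remove the case for a sensitivity analysis, since unknown timing did not lead the protocol to widen the nemolizumab window.

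A reader might go further. Misoprostol is in Appendix B with no limit on timing or setting, and Section 7.2.2 says that the EHR data include "drug prescription (including number of refills) and administration data". From this one might infer that births with misoprostol given at delivery would be dropped in Market Clarity but kept in the claims database, with a large loss from the 214 infants. The documents do not support that. Section 7.2.2 describes what the database holds. Section 7.4.3 states that, unless otherwise specified, prescription medications are identified through pharmacy dispensings, which a labour-ward dose is not, and limits on route or setting may come with the SAP code lists. The protocol gives no rate of such use. The 214 is the requirement for the whole study across sources, so an assumed loss in EHR-linked sources cannot be applied to all of it.

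**Conclusion.** The chromosomal/syndromic mismatch holds on the text. The protocol excludes a cause but closes the exclusion before it stops counting cases, and nothing elsewhere corrects this. The consequence is modest: a true RR of 2.5 would appear as about 2.49–2.42. This rests on two assumptions, that 1–6% of counted MCMs are affected and that late coding is equally frequent in the groups compared. The stated sample size is right on its own inputs. The reason to act is that the definition of a primary outcome case should not depend on when a diagnosis was coded.

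The teratogen window is a secondary point. It does outlast the protocol's MCM exposure window and does condition on post-entry events, but whether to shorten it in the main analysis is a trade-off. The size and direction of any effect cannot be derived from the document. It would go too far to conclude that the rule removes a large or source-dependent share of births, or that later exposure to a listed drug can never matter for a malformation.

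**What to change.** 1. In Section 7.3.3.3, extend the chromosomal/syndromic exclusion to codes on the infant record through the same follow-up as MCMs: up to one year, with the same censoring as Table 2. State whether syndromic includes the Q87 group listed in Appendix E. The cost is a wording change. Infants censored early have less time to receive a late chromosomal code, but the same holds for MCM codes, so the two windows stay aligned.

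2. Keep the teratogen exclusion through the end of pregnancy as the main rule if preferred. Add to Section 7.7.3.5 a sensitivity analysis for MCM that ends the teratogen window at LMP + 97 days, and report how many pregnancies per cohort and data source are excluded only for later exposure. The cost is one further analysis run. Pregnancies with late exposure to drugs that may act after the first trimester would enter only this sensitivity analysis.

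Data extraction for the final report is planned to begin in December 2032 (Section 4), so both changes can be made well beforehand.

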7.3.4 Identification of Moderate to Severe AD

Women will be considered to have moderate to severe AD if they meet one of the following criteria between 12 months prior to ECD and the end of pregnancy:

1. ≥ 2 claims with an AD diagnosis code (ICD-10-CM: L20*), at least 30 days apart, from any physician and ≥ 1 dispensing of nemolizumab, dupilumab, abrocitinib, upadacitinib, baricitinib, tralokinumab, or lebrikizumab; OR
2. ≥ 2 claims with an AD diagnosis code, at least 30 days apart, from any physician and ≥ 2 dispensings on different days of high potency topical corticosteroids or systemic immunosuppressants; OR
3. ≥ 2 claims with an AD diagnosis code, at least 30 days apart, from a dermatologist or allergist and ≥ 3 dispensings on different days of medium potency topical corticosteroids, topical tacrolimus, phototherapy, or oral/parenteral corticosteroids.

In a validation study, a similar algorithm had a positive predictive value (PPV) of 76% (95% confidence interval [CI] 53%, 90%; [Chomistek et al., 2023a](#)). Nemolizumab, abrocitinib, upadacitinib, baricitinib, tralokinumab, and lebrikizumab were not included in the validation study because they were not approved for moderate to severe AD at the time of algorithm development. A full list of diagnosis codes and drugs included in this algorithm can be found in [Appendix C](#).

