For the final report, pregnancies exposed to nemolizumab and their matched comparators will be identified in the selected databases. The final report analyses will employ a target trial emulation approach using a sequential matched cohort design that aligns cohort entry by gestational week (Caniglia et al., 2023; Hernández-Díaz et al., 2023). Nemolizumab-exposed pregnancies will be 1:4 matched to comparator pregnancies based on maternal age at cohort entry, gestational week of dispensing, indication, and calendar week. The frequency of pregnancy and infant outcomes among nemolizumab-exposed pregnancies and comparator pregnancies will be calculated. In the comparative analysis, pregnancies among patients with moderate to severe AD or PN who were

exposed to nemolizumab will be contrasted with the comparator groups using stabilized inverse probability of treatment weighting (IPTW) to adjust for potential confounding. RRs will be estimated using robust Poisson regression models and HRs using Cox proportional hazards models.

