7.3.2 Inclusion Criteria

Pregnancies among women who meet the following criteria will be eligible for inclusion in the study:

- An ECD between 12 August 2024 and 31 March 2032
- For claims data sources, continuous health plan enrollment with complete medical and pharmacy benefit coverage from 6 months before and including cohort entry (only applicable to the pregnant woman)
- For linked claims-EHR data sources:
 - Pharmacy (but not medical) coverage during the full pregnancy period (as described in [Table 1](#)) will be required to ensure dispensings of cohort defining drugs are captured. (A shorter period of continuous enrollment will be required for linked claims-EHR data sources compared with the claims databases because pharmacy claims will be used primarily for exposure assessment, while covariates will be assessed from the EHR data).
 - Presence of at least one outpatient clinical visit at least 6 months prior cohort entry (to establish a 6-month baseline period for assessment of AD and PN as well as clinical covariates).
- Evidence of moderate to severe AD or PN ascertained using appropriate algorithms

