7.3.5 Identification of PN

Pregnant women will be considered to have PN if they have at least two ICD-10-CM diagnosis codes for PN (L28.1), at least 30 days apart, between 12 months prior to pregnancy and the end of pregnancy. In a validation study, this algorithm had a PPV of 87.9% (95% CI 81.5%, 94.3%; [Roh et al., 2022](#)).

Although nemolizumab is approved for the treatment of overall PN in the US, it is authorized for the treatment of moderate to severe PN in Europe. Currently, there is not a published, validated algorithm for moderate to severe PN. Optum will continue to search the published literature over the course of the study to see if a validated claims-based algorithm for moderate to severe PN is published. If a validated algorithm is found that has suitable performance characteristics, the methods for identifying PN may be modified.

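### AD/PN eligibility can be met by claims after cohort entry, which drops early losses from all three cohorts and can bias nemolizumab versus unexposed in AD

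*Protocol*

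**What the plan says.** Section 7.3.4 counts a woman as having moderate to severe AD "if they meet one of the following criteria between 12 months prior to ECD and the end of pregnancy". Each criterion needs two AD claims at least 30 days apart, plus treatment evidence:

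- Criterion 1: "≥ 1 dispensing of nemolizumab, dupilumab, abrocitinib, upadacitinib, baricitinib, tralokinumab, or lebrikizumab".
- Criterion 2: "≥ 2 dispensings on different days of high potency topical corticosteroids or systemic immunosuppressants".
- Criterion 3: "≥ 3 dispensings on different days of medium potency topical corticosteroids, topical tacrolimus, phototherapy, or oral/parenteral corticosteroids", with the AD claims coming from a dermatologist or allergist.

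For PN, section 7.3.5 asks for two codes "at least 30 days apart, between 12 months prior to pregnancy and the end of pregnancy" and no treatment. Section 7.3.2 makes AD or PN an inclusion criterion.

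Time zero is the gestational week of entry. The worked example in section 7.3.6.1 reads "Cohort entry among the Week 8 nemolizumab and comparator cohorts will be set to 8 weeks' + 0 days". Table 2 starts follow-up for ectopic pregnancy, elective termination and spontaneous abortion at cohort entry. Section 7.1 states the intent: "The final report analyses will employ a target trial emulation approach using a sequential matched cohort design".

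Sections 7.3.2 and 7.3.6.6 speak of AD and PN as baseline assessments, and section 7.7.3.1 restricts propensity score covariates to entry or earlier. No section requires the AD/PN criteria to be met by entry.

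For linked claims-EHR sources, section 7.3.2 also requires "Pharmacy (but not medical) coverage during the full pregnancy period". Table 1 ends that period at the pregnancy outcome.

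**The concern.** In a target trial emulation, eligibility has to be known at time zero. Here it can be conferred later, and the time available for that is set by how long the pregnancy lasts, which is the outcome itself. A woman who is one AD code or one dispensing short at entry is kept if her pregnancy continues until the missing claim appears, and is dropped if she miscarries first.

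Two objectives are at stake. The frequency objective suffers because early losses are under-counted in every cohort. The comparative objective suffers if the under-counting differs between cohorts, and in AD there is a reason for it to differ between nemolizumab and unexposed pregnancies.

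Nothing planned repairs this. Weighting uses information up to entry, none of the analyses in section 7.7.3.5 varies the eligibility window, and section 7.10 does not mention the issue. Indication is also a matching factor, so matching too could draw on later claims.

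**Working it through.** **1. The plan's own figure.** Table 3 gives 77 exposed pregnancies for spontaneous abortion (14% risk, RR 2, 1:4 ratio, 80% power, two-sided 0.05). The Fleiss formula without continuity correction is n = [1.96·√(1.25·p̄·q̄) + 0.8416·√(p₁q₁ + p₀q₀/4)]² / (p₁ − p₀)². With p₁ = 0.28, p₀ = 0.14 and p̄ = (0.28 + 4·0.14)/5 = 0.168, this gives (0.819 + 0.405)²/0.0196 = 76.5, so 77. The figure reproduces. The point below does not depend on it and uses only the 14%.

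**2. Length of the eligibility window.** With ECD at gestational week 2, the window for a pregnancy ending at week w is 365 + 7(w − 2) days. After entry at week 6 (chosen for illustration), 7(w − 6) days remain.

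| Pregnancy ends at week | Whole window (days) | Days left after entry at week 6 |
|---|---|---|
| 8 | 407 | 14 |
| 12 | 435 | 42 |
| 20 | 491 | 98 |
| 40 | 631 | 238 |

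A woman with no AD code at entry who loses the pregnancy at week 8 cannot qualify at all, since 14 days is shorter than the 30 days required between codes.

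**3. Treatment evidence by cohort (AD).** A nemolizumab user, or a user of dupilumab, lebrikizumab or tralokinumab, meets the drug part of criterion 1 with the index dispensing. An unexposed woman will usually need two dispensings (criterion 2) or three (criterion 3). All need two AD codes.

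**4. Upper-type illustration.** Assume 14% spontaneous abortion in both groups, every exposed woman already qualified at entry, and a share u of potential unexposed women who qualify only after the loss period. The protocol gives no u. The unexposed risk then appears as 0.14(1 − u) / [(1 − u) + 0.86u], and the apparent RR is 0.14 divided by this.

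- u = 10%: 0.126/0.986 = 12.8%; RR 1.10.
- u = 20%: 0.112/0.972 = 11.5%; RR 1.215, rounded to 1.22.
- u = 30%: 0.098/0.958 = 10.2%; RR 1.37.

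With 352 exposed and 1,408 comparator pregnancies, the approximate chance of a falsely significant excess, on unweighted proportions, is 9%, 26% and 52%.

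**5. Letting exposed women lose early losses too.** This is a simulation with no true effect. It assumes entry at week 6, 14% loss spread evenly over weeks 6 to 20, and equal rates in all cohorts of 1 to 4 AD codes and 1 to 4 qualifying dispensings per year. These rates are assumptions.

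| Window | Nemolizumab risk | Unexposed risk, criterion 2 | Unexposed risk, criterion 3 | RR, criterion 2 | RR, criterion 3 |
|---|---|---|---|---|---|
| As written | 9.4–13.4% | 6.7–12.9% | 5.1–12.1% | 1.02–1.44 | 1.11–1.85 |

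With the window closed at entry, checked for the two-code rule alone and for criterion 2, the risk is about 14% and the RR about 1.0. Active-comparator users follow the same rule as nemolizumab users, so with equal coding rates their ratio is 1.0 by construction.

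**The case against.** The case for leaving the window open is that two scattered codes are hard to collect, section 7.3.6.6 grants the 12-month look-back only as data allow, and exposed pregnancies are scarce. That explains the choice but does not remove the selection. Four limits on the point do stand.

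- A reader might infer that nemolizumab pregnancies keep their early losses while both comparators lose theirs. The text does not support this. Criterion 1 needs two AD codes that the index dispensing does not supply, so exposed early losses are dropped too. The active comparator qualifies by the same criterion, and PN needs codes only. Those contrasts are distorted only if coding patterns differ between cohorts.
- A reader might infer that no early loss can qualify, or that every unexposed woman must collect two or three dispensings. Women who met the criteria before entry are unaffected. The unexposed definition bars biologics only from five half-lives before ECD, so an earlier dupilumab dispensing within the 12 months can satisfy criterion 1.
- A reader might extend the bias to the primary outcome. Malformations are assessed in linked live births, all of which reached delivery, so the early-loss mechanism barely operates there.
- A reader might count the full-pregnancy pharmacy coverage rule as more of the same. It is a post-entry condition, but because it ends at the pregnancy outcome, a short pregnancy meets it more easily. It works in the opposite direction and applies to all three cohorts.

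**Conclusion.** The point holds in this form. As written, sections 7.3.4 and 7.3.5 allow selection on pregnancy duration after time zero, against the design stated in section 7.1. Frequencies of spontaneous abortion, elective termination and ectopic pregnancy are understated in all three cohorts. The nemolizumab versus unexposed hazard ratio in AD can be biased upward for these outcomes.

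The size is unknown, because the protocol gives neither coding rates nor the share of women who qualify only after entry. The ratios of 1.10 to 1.37 lean high because they treat every exposed woman as qualified at entry and place all late qualification after the loss period. The simulated range reaches from almost nothing (1.02) to substantial (1.85), depending on assumed rates and on which criterion the unexposed women use. All these are risk ratios, whereas the plan uses Cox models for these outcomes. The Table 3 sample sizes are not wrong on this account.

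**What to change.** - **Sections 7.3.4 and 7.3.5:** require the criteria to be met between 12 months before ECD and the cohort entry week, counting the index dispensing, identically in all three cohorts and reassessed at each weekly cohort.
- **Sections 7.3.2 and 7.3.6.6:** align the wording with this, so that AD/PN status is a baseline item throughout.
- **Section 7.7.3.5:** keep the present window, open to the end of pregnancy, as a sensitivity analysis. Reporting by cohort how many pregnancies qualify only after entry would show how much the choice matters.
- **Section 7.3.2, linked claims-EHR sources:** as a separate change, require pharmacy coverage through the entry week and censor at loss of coverage, as the claims sources do.

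The work is wording and programming, and data extraction for the final report is planned to start only on 08 December 2032. The cost is in numbers. The unexposed pool shrinks, although a woman who qualifies later can join a later weekly cohort. An exposed woman whose second code follows her first dispensing cannot, because her entry is fixed at the first dose, so she leaves the primary analysis. That matters in a scarce arm: Table 4, given for information only, shows 209 AD pregnancies with a dupilumab dispensing over 2020–2024 (2024 incomplete), against a target of 352 nemolizumab-exposed pregnancies.
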